Determinants of health for older age groups Changes to young people's travel behaviour could be hypothesised to have consequent effects on health and the determinants of health for other population groups. If larger numbers of young people are using buses, this may reduce willingness to travel for other users, either through direct exclusion (if buses are too full) or through 'fear-based exclusion', with elderly people in particular reported to be concerned about personal safety and security (DfT 1999). The extension of free travel to under 18 year olds has exacerbated public concern about criminal damage, anti-social behaviour and assaults on buses, although it has been difficult to identify whether incidents have actually increased (London Assembly 2008). Concerns about young people and their contribution to 'fear based exclusion' are certainly not new (DfT 1999), but it is unclear whether extending free travel for young people has contributed to reductions in wider population use of the bus network. Using travel diary data, we will examine transport modal shifts in other age groups to identify trends over time in active transport. Qualitative research with older citizens will explore their accounts of links between young people's access and their own bus use.

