To assess the public health impact of free bus travel we need first to identify changes in travel behaviour, to estimate the impact on a key **determinant of health** (active transport) and on potential travel exclusion for both young people themselves, and for other age groups in the population. Second, we need to identify changes to injury rates for 12-15 and 16-17 year olds before and after Sept 2005 and 2006 respectively in order to estimate the impact on **direct health outcomes** for these age groups. We then need to account as far as possible for confounders through appropriate population, place and time comparisons. With robust estimates of the effects on injury and active transport, we can then develop methods for economic evaluation. The objectives of the study are therefore to:

- 1. Determine the causal pathways that plausibly link transport interventions and young people's health;
- Identify the ways in which young people and older citizens understand the role of bus and other transport mode access in facilitating and constraining their wellbeing;
- 3. Assess the impact of free bus travel for 12-17 year olds on their use of bus and other transport modes;
- 4. Assess the impact of free bus travel for 12-17 year olds on the use of bus and other transport modes by older age population groups;
- 5. Identify changes in the incidence of injury in young people after they had access to free bus travel;

6. Investigate, develop and apply a method for conducting an economic evaluation of the health impacts from introducing free bus travel for young people in London and other similar social interventions.

4. Research design

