The general design of this evaluation equates to an untreated control group design with pre- and post-test in Cook and Campbell's terminology, which they note is the most frequently-used interpretable quasi-experimental design. However, within each aim (see below) we propose methods to increase the credibility of causal inference. These will utilise best practice in the design and analysis of observational studies to minimise threats from confounding, and increase the credibility of causal attribution. We will examine aspects of internal consistency of evidence (whether intervention effects are similar in different age groups, and across more than one outcome); specificity (facilitated by comparison of changes in London with other cities and in London taking account of national background trends); and coherence (addressed through cross-reference to existing studies and knowledge of the determinants of active travel, and through the new qualitative data). Evidence for some outcomes (eg injuries) will be stronger, given there is sufficient data to conduct interrupted time series analyses. Causality is also determined by the observed strength of association which will be assessed at the analysis stage. Glasziou (2007) and others for example provide guidance on the interpretation of effect size data from observational studies when RCTs are not possible. The examination of Dose-Response relationships will strengthen the credibility of interpretation, and these will be estimated by the use of proxy measures of bus access, such as SOA level Public Transport Accessibility Levels. Qualitative data derived from a range of stakeholders will also permit examination of "local history" explanations for any observed differences. GIS methods will be used to describe in detail the transport environment across the study area.

4.2.Methods

4.2.1 Methods - Aim 1

To determine the causal pathways that may plausibly link transport interventions and young people's health.

In addition to adding to much needed evidence in the field of transport, this study will contribute to methodological development by: identifying and reviewing available and

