Quantitative data series are available for London on use of transport, including walking and cycling (London Area Travel Survey (LATS), London Travel Demand Survey (LTDS)), and injuries (Stats19 road injury data, Hospital Episode Statistics (HES)). These allow analyses of change in important outcomes following the introduction of the free bus and tram travel scheme. The quantification of change will be based on before-after comparisons using two time points: (i) the introduction of free bus travel in London to children <16 years in September 2005 and (ii) its extension to those under 18 years in September 2006. To minimize possible bias arising from changes over time in the completeness of data recording, for most analyses we propose to compare the changes in the relevant outcomes in the under 18s (under 16s) with those observed at other ages: a *change-on-change* analysis. Although this carries some penalty in terms of statistical power, the comparatively large number of events at other ages means the penalty is modest, while achieving a gain of reduced potential for bias. We will examine the following outcomes:

- the frequency and distance of active transport (i.e. walking and cycling) in those aged 12–17 years;
- the frequency of **bus use and the distance travelled by bus**, in those aged 12–15 and 16–17 years;
- the frequency of bus travel and the distance travelled by bus in other age groups;
- the **incidence of intentional and non-intentional injuries** in young people aged 12-17.

Table 1: Available sample sizes of main secondary data sets

Table 1. Available	Sample	31203 01	main sc	, con luar y	uala se	,10			
	2001	2002	2003	2004	2005	2006	2007	2008	
FREE BUS/TRAM					<16s	<18s			
SCHEME									
		Pre-inte	rvention		Post-intervention periods				
London Area									
Travel									
Survey	30,000								
(LATS)	30,000								
[number of									
households]									
London Travel &									
Demand Survey					5,000	8,000	8,000	8,000	
(LTDS) [number of					3,000	8,000	8,000	8,000	
households]									
National Travel									
Surveys (NTS)	9,000	9,000	9,000	9,000	9,000	9,000	9,000		
[number of	3,000					3,000	3,000		
households]									
Stats19 [persons]	45,000	41,000	39,000	35,000	32,000	29,000	Not yet	Not yet	
(percent in 12-17	(7%)	(7%)	(7%)	(7%)	(7%)	(6%)	analysed	analysed	
years)									
Hospital Episode	100k	100k	100k	100k	100k	100k	100k	100k	
Statistics	(350)	(350)	(350)	(350)	(350)	(350)	(350)	(350)	
(external cause									

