Analysis. For all outcomes, the principal analysis will be the comparison of the change before and after September 2005 (for those aged 12-15), and before and after September 2006 (for those aged 16–17 years). These changes will be compared with similarly-defined change at other ages. Where relevant, appropriate denominator populations (ONS population projections) will be used to allow for differences between years in the number of young people at risk. Robust standard errors will be calculated, clustering on borough to allow for similarities of outcome at that geographical level. We will also explore the use of other multi-level modelling methods to allow for other forms of data hierarchy relating to spatial variation in bus service provision.

To assess the impact of the interventions on transport (including active transport) we will compare mean times and distances, as well as the percentage of short distance trips travelled by the relevant mode (walking, cycling, bus, car). We will also estimate changes in amounts of travel on journeys to work or school in people aged under 18 years (to assess potential increased access to education).

For all outcomes, we will investigate evidence for variations by socio-economic group or household income and, where possible, by ethnicity (to address questions of impact on inequalities), although power will be limited for most such sub-group analyses.

Sample size Example of power to detect changes in distance of trips made by bus and walking

Provisional 2001 estimates of the distances of trips made by young people by bus and by walking are shown below. With 3,000 young people in the sample before and after the intervention, the study will have 80% power to detect a 10% reduction in the average daily distances walked by young people (from an average 0.91 km per day to 0.82 km per day) at a 5% significance level. Similarly, the study would have 98% power to detect a 10% increase in the distance of bus travel from an average of 4.33 km per day to an average 4.76 km per day. For transport-related injury, the study would have 80% power to detect a 10% change, or 90% power to detect a 12% change significant at the 5% level. Statistical power is inevitably more limited for subgroup analyses, but for example there is 90% power to detect a 15% change in average distance travelled by bus by young people within the most deprived quartile.

Table 2: Average distances by mode for Londoners aged 12-17 years (LATS 2001)

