This evaluation methodology will allow the research team to assess whether the policy has had an overall positive economic impact when compared with the costs and benefits based on the inputs that can be monetised for public health. It will then, in combination with the qualitative and quantitative assessments, provide an impact assessment of the policy with regard to public health. This approach of combining both a value for money assessment alongside other impacts that are assessed either qualitatively or quantitatively is common practice in transport policy evaluation (DfT 2005c), and this study provides an opportunity to identify the utility of this approach within public health evaluations.

5. Study population

The primary study population is residents of London aged 12-17 years old. However, as other groups will be affected by the intervention, the wider study population is all residents of London aged over 12. Populations for specific objectives are detailed above (Section 4.2).

6. The intervention

The intervention is the introduction of free bus travel for young people under 16 years old in September 2005 and those under 18 years old (in full time education or unwaged training) in September 2006.

7. Outcome measures

Key outcome measures investigated in this study are:

- reported health benefits and risks of access to bus travel for young people and older citizens;
- change in the time and distance of active transport (walking, cycling) undertaken by young people and older age groups;
- change in road transport injuries in young people;
- change in assault injuries in young people.

In addition, our review of the literature and available evidence will identify existing evidence on the following outcome measures:

- Changes in access to education and training for 16-18 year olds;
- Changes in active recreational activity;
- Changes in bus incidents.

These are detailed in the methods section (4.2) above.

8 – 10. Assessment and follow up; sample sizes; statistical analysis

Assessment of outcomes, sample sizes and analyses are all detailed under methods for specific components, above (Section 4.2)

11. Ethical arrangements

The study will be conducted in accordance with MRC guidelines, those of LSHTM and good practice for social research (the ESRC ethical framework). Approval from

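### The main travel contrast uses other ages in London as an untreated control although the protocol expects them to be affected, so for Aim 3 it estimates the youth effect minus any spillover

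*Protocol*

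**What the plan says.** The opening of section 4.2.3 of the protocol plans, for most analyses, to "compare the changes in the relevant outcomes in the under 18s (under 16s) with those observed at other ages". The reason given is protection against changes over time in the completeness of recording. The Analysis paragraph of that section makes the rule general: "For all outcomes, the principal analysis will be the comparison of the change before and after September 2005 (for those aged 12-15", with September 2006 as the date for 16-17s, and then "These changes will be compared with similarly-defined change at other ages". Section 4.1 says that the overall design "equates to an untreated control group design with pre- and post-test".

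Other parts of the protocol treat the same ages as possibly or actually affected:

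- Section 2.2, on older age groups: if more young people use buses, "this may reduce willingness to travel for other users", through crowding or fear.
- Section 3: the fourth objective concerns the effect of the scheme "on the use of bus and other transport modes by older age population groups".
- Section 4.2.3 lists bus travel in other age groups as an outcome.
- Section 5 widens the study population to all residents over 12 "as other groups will be affected by the intervention".

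Nowhere are the control ages defined or restricted, and nowhere is spillover dealt with in the age contrast. The NTS is planned as an additional comparison for travel patterns, covering the country and other urban areas, with no stated estimator.

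**The concern.** A change-on-change estimate equals the effect in the young only if the comparison group is untouched by the intervention. Here the comparison group is also the group in which the protocol looks for displacement. If older Londoners leave the buses because young people fill them, the age contrast credits that fall to the young as extra bus use. More data do not help, because this is bias and not imprecision.

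Two further points follow. The same contrast cannot by itself say whether older people were displaced (Aim 4). And for 12-15s, other ages as written includes 16-17s, who received free travel a year later. Aims 3 and 4 both feed the economic evaluation, so a displacement effect could enter it twice.

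**Working it through.** **1. The protocol's own power figures.** Inputs from section 4.2.3 (sample size paragraph and Table 2): 3,000 young people before and 3,000 after; walking 0.91 to 0.82 km, SD 1.26; bus 4.33 to 4.76 km, SD 4.1; 5% level, taken as two-sided. Power = Φ(δ / (SD·√(2/3000)) − 1.96).

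- Walking: 0.09 / 0.03253 = 2.766, power 79.0% (79.9% with δ = 0.091). Stated: 80%.
- Bus: 0.43 / 0.10586 = 4.062, power 98.2%. Stated: 98%.

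The figures reproduce, but as a plain before-after comparison in the young. Table 2 labels these distances as per trip and the text as per day; they are used here as the text uses them.

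**2. Adding the control.** Other ages: 67,252 − 5,450 = 61,802 in the 2001 London Area Transport Survey (LATS) and 47,000 − 3,000 = 44,000 in the later London Travel Demand Survey (LTDS). For bus, SE = 4.1·√(1/3000 + 1/3000 + 1/61,802 + 1/44,000) = 0.109 km. Power becomes 97.7% for bus and 76.7% for walking. This agrees with the protocol that the penalty is modest, so precision is not the problem.

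**3. What the contrast estimates.** Let g be the background change common to all ages, τ the effect in the young and s the spillover at other ages.

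- Change in the young: g + τ.
- Change at other ages: g + s.
- Difference: τ − s.

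**4. Size for bus distance.** Assumptions: τ = +10% (0.433 km); other ages have the same baseline and SD as the young; s ranges over −5% to +5%, because the documents give no value.

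| Spillover s | Aim 3 estimate (km) | As % of 4.33 km |
|---|---|---|
| −5% | 0.65 | 15 |
| −2% | 0.52 | 12 |
| 0 | 0.43 | 10 |
| +2% | 0.35 | 8 |
| +5% | 0.22 | 5 |

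On a ratio scale the −2% row is 1.10 / 0.98 − 1 = 12.2%. If τ = 0, a 2% spillover (0.0866 km, 0.80 SE) gives a significant result 12.5% of the time, and a 5% spillover (0.2165 km, 1.99 SE) gives one 51% of the time, against a nominal 5%. Clustering is ignored, as it appears to be in the stated power; a larger SE would lower these two rates but leave the bias unchanged.

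**5. What the NTS adds.** Let b be bus growth specific to London and d any artefact of the change from LATS to LTDS, both taken as equal across ages.

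- London versus other urban areas, older ages: s + b + d.
- The same contrast, young ages: τ + b + d.

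The first gives s only if b + d is near zero. Subtracting one from the other returns τ − s. The two kinds of contrast thus fail in different ways, which is the reason to report both.

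**6. 16-17s in the control for 12-15s.** In LATS they are 2,300 of 67,252 − 3,150 = 64,102 at other ages, or 3.6%. With equal baseline use, a 10% effect in them moves an all-ages control by 0.036 × 10 = 0.4 percentage points. If a control of adjacent ages were half 16-17s, it would move by 0.5 × 10 = 5 points.

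**The case against.** Four objections carry weight.

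First, a reader might infer that Aim 4 is simply Aim 3 with the sign reversed and so cannot be answered. The protocol never writes that contrast. Section 2.2 describes trends over time in other age groups, and sections 1, 4.1 and 4.2.3 plan comparisons with national data, other cities and other urban areas. What stands is narrower: the age contrast alone cannot identify Aim 4, and no estimator is given for the comparison that could.

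Second, one might infer that the bias always runs away from zero and reaches every outcome. The documents do not support that. The direction is clear for bus use if youth use rises and other use falls. For walking, section 2.2 allows either sign in the young, and the bias depends on how displaced trips are made. The spillover hypothesis concerns travel, not injury at other ages, and the hospital data also have unrelated external causes as a comparator.

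Third, it is tempting to make the NTS the principal comparator. The age contrast was chosen to cancel changes in recording, and the London instrument switches from LATS to LTDS between before and after. Section 2.3 says bus transport grew faster in London than elsewhere. An NTS contrast would credit both to the scheme, and could hide displacement of older people. This objection stands.

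Fourth, the spillover sizes are invented for illustration, and section 2.2 itself says it is unclear whether wider bus use fell. That is right, and it limits the claim to a rate of bias per unit of spillover.

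**Conclusion.** The point holds for the Aim 3 travel outcomes, chiefly bus use. The principal contrast estimates the youth effect minus the spillover, while the protocol both calls the control untreated and expects it to be affected. Bias is about one percentage point in the youth bus estimate per 1% change in bus use at other ages, upward if that use falls. This assumes similar baseline use in both groups and a common background trend. Against a design powered for 10% changes, a spillover of a few percent would matter; whether there was one is unknown.

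Treated 16-17s in the control for 12-15s have a small effect in an all-ages control (about 0.4 points for a 10% effect) and a larger one with adjacent ages. The point does not extend to the Aim 5 injury outcomes, except that treated 16-17s should also leave the under-16 comparator there.

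**What to change.** 1. **Aim 3.** Keep the within-London age contrast as principal, but define the control as the ages least likely to be displaced, for example 25-59, leaving out 60 and over. Use 16-17s as comparator for 12-15s only from September 2005 to August 2006. Crowding can affect any age, so this reduces the spillover but may not remove it.
2. **Aim 4.** Do not use the contrast of young against older people. Estimate the before-after change at older ages in London against the same ages in other urban areas from the NTS, stating that the LATS-to-LTDS change and London-specific bus growth do not cancel in it.
3. **Reporting.** Show the same-age NTS contrast beside the age contrast for Aim 3, and state that the age contrast estimates youth effect minus spillover.

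The NTS should not replace the within-London contrast as principal.

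Cost: somewhat wider intervals, because the control is smaller and the NTS has about 9,000 households a year for the whole country, and more analysis of NTS data. Section 11 does not list the NTS among the datasets accessed directly, so access to person-level records should be confirmed. The one-year window for 16-17s falls partly in 2005, when LTDS had 5,000 households and not 8,000, so that comparison will be imprecise.

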admissions in									
London)									

Travel patterns: LATS, LTDS. We will use data collected five years before the interventions in the 2001 London Area Transport Survey (LATS), and data from the 2005–2007 London Travel Demand Surveys (LTDS) for the post-interventions period. The LATS and LTDS surveys collect comparable travel data sets based on daily travel diaries, using comparable sampling designs. The 2001 LATS included 30,000 households and LTDS included 5,000 households in 2005, with a further 8,000 households annually since 2006. Every person aged over 5 years living in each household is asked to complete a one-day travel diary that records the starts, interchanges and ends of every trip made on that day. In 2001 LATS there were 360,389 interchanges (parts of trips) made by 67,252 individuals. With similar levels of travel in 2005–2008 we expect data to be available on over 250,000 travel interchanges made by 47,000 individuals. Journey times are collected in both LATS and LTDS. Journey distance is estimated using the start-point, interchange and endpoint of each trip (these locations are geo-coded and 'crow-fly' distances are easily calculated). For the travel patterns, comparisons will also be made with data from the National Travel Survey (NTS, Department for Transport). This national survey includes samples of approximately 9,000 households each year, including

approximately 20,000 individuals, with data from seven day travel diaries for each individual. The inclusion of NTS data will enable us to assess whether trends in main travel modes nationally and in other urban areas differ to those used as main modes in London.

Travel-related injuries and assaults: Stats19, bus incident reports, HES. **STATS19 road injury data,** the official dataset of human death and personal injuries from road traffic crashes on the public highway in the UK, are available for each year of the study (to 2009). We will analyse casualties among young people travelling as pedestrians, cyclists, car occupants and bus occupants, and by severity of injury ('Fatal' or 'Serious' (hospital admission), and 'Slight' - minor injuries).

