STATS19 data remain the richest source of information on road traffic injuries in England, and are an essential component of assessments of transport effects on injury events. Although there is recognised to be a degree of under-reporting in STATS19 data, the completeness in London is estimated to be around 87%, and the change-on-change analysis will help to minimize bias arising from year-to-year variations in completeness. Comparatively long series of Stats19 data are available and our experience has demonstrated the value of using these longer series, stratified by key factors, to derive more accurate estimates of the relevant trends and step effects. Differences in these between socio-demographic strata within London are likely to be an important element of the interpretation of the quantitative data. Published analyses of national data will be used to estimate national and urban area background trends in injury rates.

The utility of **bus incident reports** and other data sets will be examined for the potential to identify changes in assaults, if the known problems of reporting bias can be addressed. If feasible methods for evaluating transport interventions are to be developed, it is essential to generate knowledge about the uses and limitations of routine data sets for evaluating outcomes.

An extract of **Hospital Episode Statistics** (HES) will be obtained for England covering the period 2001 to 2009. We will identify all London residents using census super output area (SOA) code of residence. We will analyse hospital admissions due to all ICD external causes of injury, and specifically those external causes directly influenced by transport access (e.g. transport injuries, assaults). Comparisons will be made with admissions for other external causes that are not plausibly linked to transport policy change (e.g. poisoning, falls, self-harm). We will include all admissions, given that restricting our case definition by injury severity will greatly reduce the sample size available, but will conduct a sensitivity analysis using only severe injury admissions to test whether differential admission rates by external cause over time may have introduced bias (e.g. due to differences in admissions policy).

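### The supplementary background trend for road injury comes from published national analyses that need not exclude London or match the study's age bands and September dates, so the specificity check may be attenuated or mismatched

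*Protocol*

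**What the plan says.** All references are to the protocol.

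- **Source of the background trend.** Section 4.2.3, under travel-related injuries and assaults: "Published analyses of national data will be used to estimate national and urban area background trends in injury rates". The sentence names no publication and sets no condition on area, age band or date.
- **The dataset itself.** The same part of 4.2.3 describes STATS19 as "the official dataset of human death and personal injuries from road traffic crashes on the public highway in the UK" and says it is available for every study year, to 2009.
- **Principal comparison.** The opening of 4.2.3 proposes, for most analyses, to "compare the changes in the relevant outcomes in the under 18s (under 16s) with those observed at other ages". The Analysis paragraph sets the cut at September 2005 for ages 12-15 and September 2006 for ages 16-17, and adds: "These changes will be compared with similarly-defined change at other ages".
- **Role of place comparisons.** Section 4.1 bases specificity on "comparison of changes in London with other cities and in London taking account of national background trends". Section 1 uses national data and other cities, together with unaffected ages, to separate the policy from background change in injury. Section 2 lists comparable national data among the strengths of the case study.
- **Travel outcomes.** Section 4.2.3, under travel patterns, brings in the National Travel Survey (NTS) to "assess whether trends in main travel modes nationally and in other urban areas differ" from those in London.

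**The concern.** The comparison with places outside London asks whether the same ages, at the same dates, changed in the same way where the scheme did not operate. It helps with two things that an age contrast inside London handles less well. One is another London change that affected the same ages. The other is spillover to the comparison ages, which section 2.2 raises as a possibility and which objective 4 in section 3 sets out to measure for travel.

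Published analyses suit that purpose only if they happen to be tabulated in the right way. A national total ordinarily contains London, so part of any London effect would sit in the benchmark and be subtracted from itself. If the tables are not split at 12-15 and 16-17 with comparison ages, or not cut at the two September dates, the planned change-on-change cannot be repeated elsewhere. At stake is the strength of the specificity evidence for road injury, not the principal estimate.

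**Working it through.** **The plan's own figure.** The only figure attached to the injury outcome is power: 80% for a 10% change and 90% for a 12% change, at the 5% level. No event count or comparator is given, so it cannot be rebuilt from inputs. The two statements can be checked against each other. On a linear scale with a two-sided test, 80% power at 10% implies SE = 0.10 / (1.960 + 0.842) = 0.0357. Power at 12% is then Φ(0.12/0.0357 - 1.960) = 92%, close to the stated 90%. Neither figure depends on the national benchmark, and neither is disputed here.

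**Inputs for the dilution.**

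- True effect in London: a 10% reduction (RR 0.90), the size used in the power statement.
- London's share of the benchmark, s: not in the documents; assumed 5% to 25%.
- Ages 12-17 as a share of London STATS19 casualties: 7% in 2001-2005 and 6% in 2006 (Table 1).

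**Case A: the benchmark covers the treated ages only and includes London.** The London change moves the benchmark by s × 10%, so London minus benchmark recovers (1 - s) of the effect. On the ratio scale, RR observed = 0.90 / (0.90s + 1 - s):

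| s (assumed) | RR observed | Apparent reduction |
|---|---|---|
| 5% | 0.90/0.995 = 0.905 | 9.5% |
| 10% | 0.90/0.990 = 0.909 | 9.1% |
| 15% | 0.90/0.985 = 0.914 | 8.6% |
| 20% | 0.90/0.980 = 0.918 | 8.2% |
| 25% | 0.90/0.975 = 0.923 | 7.7% |

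If the stated 80% power applied to this contrast, which the protocol does not say, it would fall to about 76% at s = 5% and 56% at s = 25% (linear dilution, same SE).

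**Case B: the benchmark covers all ages and includes London.** Only the treated ages within London carry the direct effect, so the contaminated share is about 0.07 × s: 0.35% at s = 5% and 1.75% at s = 25%. At the upper end, RR observed = 0.90 / (1 - 0.10 × 0.0175) = 0.90/0.99825 = 0.902, an apparent reduction of 9.8%. The dilution is negligible, but such a series cannot supply the contrast of 12-15 and 16-17 with other ages.

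**Case C: the benchmark excludes London.** There is no dilution. Whether the contrast can be repeated still depends on the published age bands and dates.

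**Dates.** If the published series were by calendar year (an assumption), January to August, 8 of 12 months or 67%, of 2005 for ages 12-15 and of 2006 for ages 16-17 would pre-date the policy.

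Cases A and B are alternatives, so the full dilution in A should not be added to the age mismatch in B.

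**The case against.** The strongest reply is that this series is not the study's control. The principal comparator is other ages, with matching dates. The wording "The general design of this evaluation equates to an untreated control group design with pre- and post-test" in section 4.1 labels the general design and is not attached to national data. A reader might infer that the study's untreated control contains the treated population; the documents do not support that.

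Nor do they support several other stronger readings:

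- **That London is certainly in the benchmark.** This is an inference from the word national. Sections 1 and 4.1 speak of other cities, and the NTS text of other urban areas, which points to London being left out of those series. The injury sentence itself says only urban area.
- **That controls outside London are the only ones outside the scheme.** Under section 6, Londoners aged 18 and over were not eligible for it. The planned England extract of Hospital Episode Statistics, with London residents identified, also makes a non-London comparison possible for admissions, and admissions for causes unrelated to transport provide a further contrast.
- **That the specificity check is void.** Over the assumed range, most of the effect survives even in Case A.

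It can also be said that a trend fitted only to pre-policy years contains no policy effect, that no passage says annual tables will be used, and that a statistical analysis plan could settle bands and dates.

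These points limit the size and standing of the concern. They do not remove it. The protocol has chosen published analyses as the source, and a later plan that keeps that choice is confined to whatever others have tabulated. The England hospital extract does not supply the police-recorded road casualties in STATS19.

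**Conclusion.** The point holds as a weak choice of method for a supporting comparison, and it is worth correcting because the correction is cheap. The principal injury analysis stands.

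The specificity check for road injury may be attenuated towards no difference, or may not match the age-and-date contrast it is meant to test. Attenuation of a true 10% reduction to about 9.5-7.7% requires three things: that London is included, that the benchmark is restricted to the treated ages, and that s lies in the assumed 5-25%. With an all-age benchmark the attenuation is negligible, and the fault is instead that the contrast cannot be repeated.

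**What to change.** Replace the sentence on published analyses in section 4.2.3. State that STATS19 records from outside London, for other cities and for the rest of the country, will be analysed for ages 12-15 and 16-17 and the same comparison ages, by month, with the same September 2005 and September 2006 cuts, and that the change-on-change will be repeated there. Keep published trends as context only.

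In the travel patterns paragraph, state that London residents are excluded from the national NTS series. The comparison with other urban areas already reads as excluding them.

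The cost is a wider extract of a dataset the team already uses, some data preparation, and reruns of the same code. The interval will be slightly wider than if a published trend were treated as known.
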